# 2) Objectives\*

The purpose of this study is to investigate the effect of balance training with transcranial direct current stimulation (tDCS) on postural balance, self-reported functions, and neural functions in individuals with chronic ankle instability (CAI).

# 3) Background\*

Ankle sprain is the most common injury in physically active individuals.[1] A significant proportion of ankle sprain patients suffer from residual symptoms and recurrent injuries, and develop a chronic disease, clinically termed as chronic ankle instability (CAI).[2-4] CAI is a multifactorial condition involving a variety of predisposing factors for CAI: muscle weakness [5], muscle activation failure [6], postural control impairments [7], and altered joint mechanics [8-9]. However, among these factors, it is well known that postural control plays an essential role in ankle instability. For this reason, discovering the underlying mechanisms of impaired postural control has been a primary focus in the CAI literature. With recent advances in neurophysiological technology, sport medicine researchers have begun to examine specific mechanisms regarding impaired postural control following ankle injuries. Recent studies [10-16] have demonstrated altered neural functions in CAI patients. Patients with CAI demonstrated deficits in spinal excitability [11, 14], cortical excitability [10, 12, 14, 15], smaller excitable cortical areas of lower leg muscle [17], and higher fluctuations of cortical activation [13] compared to healthy individuals. These findings [10-16] indicate the alteration of neural functions in patients with CAI, which may be related with postural control deficit, and clearly suggest a new therapeutic target, not just treating the ankle joint, but the brain control in CAI patients.

Balance training (BT) has been frequently used by clinicians for improving postural control in CAI patients.[18-21] However, recent research with advanced analysis techniques for postural control found that the current BT may not be ideal, as only one third of CAI patients presented clinically meaningful improvements.[22] Besides, BT was not strong enough to restore the decreased cortical activation [23] that is potentially linked to poor postural control in CAI patients. These results [22, 23] suggest that the need for potential adjunctive rehabilitation that is capable of altering the ongoing maladaptive brain plasticity in order to supplement the clinical efficacy of BT for CAI patients.

Transcranial direct current stimulation (tDCS) is an non-invasive electrical stimulation technique over the brain that safely influences the cortical excitability, and it is a painless and portable.[24-29] It is thought that a subtle electrical current (up to 2.0 mA) can induce facilitatory effects on cortical excitability of the primary motor cortex: The anodal (+) stimulation is known to increase cortical excitability while cathodal (-) stimulation decreases the excitability.[31-33] Given these positive outcomes and high applicability (safe, portable, and easy-to-use), tDCS has been extensively used in the neuroscience literature[34-38] to address neurological symptoms including impaired postural control and motor dysfunction in a wide range

of neurological patients such as stroke[38], Parkinson's disease[36], and spinal cord injury[37].

There are emerging interests in tDCS to address musculoskeletal conditions. A recent study [39] has examined its efficacy for patients with chronic low back pain and confirmed its effects on pain and postural control. Anodal tDCS was applied to the motor cortex area during 20 minutes of balance training: It was found that pain and postural control were significantly improved after the intervention (tDCS with balance training).[39] Besides, tDCS has been used in patients with CAI. The tDCS was applied to the patients before they began their strength training. The use of tDCS in combination with strength training was found superior to strength training alone CAI patients.[40] This tDCS study for CAI clearly shows that CAI patients are responsive, and raise the potential that tDCS can be incorporated into other CAI rehabilitation programs such as balance training. Thus, it is possible to hypothesize that BT with tDCS would improve postural control and patients reported outcome along with enhancement in neural excitability, which induces superior improvements to BT alone.

# 4) Inclusion and Exclusion Criteria\*

Below are characteristics of the subject population

- Anticipated number: 60 human subjects with chronic ankle instability
- Age: 18-45
- Sex: Both
- Race: All

Criteria for inclusion:

- Subjects should be neurologically sound.
- Subjects should have abilities to maintain single leg stance at least for 10 seconds.
- A history of ankle sprain
- A history of ankle joint giving ways
- Current feelings of ankle joint instability

Criteria for exclusion:

- Individuals with a clinically defined neurological disorder, with an increased risk of seizure for any reason, with a history of treatment with TMS, deep brain stimulation for any disorder will be excluded.
- Patients with cardiac pacemakers, implanted medication pumps, intracardiac lines, or acute, unstable cardiac disease, with intracranial implants (e.g. aneurysm clips, shunts, stimulators, cochlear implants, or electrodes) or any other metal object within or near the head, excluding the mouth, that cannot be safely removed will be excluded.
- A history of balance or vestibular disorder
- A history of previous surgeries to the musculoskeletal structures in either limb of the lower extremity
- A history of a fracture in either limb of the lower extremity requiring realignment

- A history of acute injuries to the lower extremity joints in the previous 3 months, which impacted joint integrity and function (i.e., sprains, fractures) resulting in at least 1 interrupted day of desired physical activity
- A history of herniated disc
- Poorly controlled headache
- Hypersensitivity to electrical or magnetic stimulation

The study will not recruit any of the special classes of subjects as shown below.

- Adults unable to consent
- Individuals who are not yet adults (infants, children, teenagers)
- Pregnant women
- Prisoner

[figure not shown]

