# 5) **Procedures Involved\***

## **Study Overview**

The proposed study is a double-blinded, randomized-control design which examines the efficacy of tDCS with balance training (BT) for patients with chronic ankle instability (CAI). Participants will be randomly allocated to one of two groups including (1) anodal tDCS + BT and (2) sham tDCS + BT. Outcome measures allow us to measure effects on postural balance, neural functions, and self-reported physical function.

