#### **Study Interventions**

Transcranial Direct Current Stimulation: Participants in the active and sham tDCS groups will receive tDCS while performing balance exercises (about 20-min application). An anodal surface electrode will be attached to the contralateral motor cortex (M1) of the CAI-involved side and the reference electrode will be placed on the ipsilateral side of the supraorbital ridge. These electrode placements (stimulation sites) were consistent with previous studies.[39, 40] Anodal tDCS will deliver a low electrical current stimulation at 2 mA, while for sham tDCS, the stimulator will be turned off automatically 30 s following the application. The sham stimulation mimics the transient scalp sensation perceived when the stimulator is initially switched on. This technique is currently state-of-the-art for conducting convincing sham stimulation in the tDCS field. For tDCS treatment set-up, participants will sit on the chair. Sponge electrodes will be placed and secured with a head strap: Active electrode over the motor cortex area and the reference electrode on the contralateral side of the upper forehead. The tDCS set-up will take approximately 10 minutes. Participants will undergo 12 sessions (20-min each) of active or sham tDCS using 2mA current. This constant current device ramps up to the desired amplitude and ramps the amplitude back to 0mA at the end of the treatment duration. tDCS (real or sham) will be delivered from beginning of balance training to the end of the training. After each training session, an aloe cream will be applied to the skin under the electrodes to reduce risks associated with skin drying. **Balance training:** All groups will receive the same progressive balance training (BT). BT will be implemented 3 times a week over 4 weeks, each training session lasting about 20 minutes. The 4 weeks of BT has been shown effective in enhancing postural control in patients with CAI. The BT will consist of 3 types of balance exercises: (A) single-leg stance exercise with eyes open and closed and on stable and unstable surfaces, (B) single-leg deadlift exercise with eves open and on stable and unstable surface, and (C) balance

exercise on wobble board. Participants will be asked to perform a progressive level of exercise in each session.

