# 8) Risks to Subjects\*

## tDCS risks and safety plan

The risks associated with tDCS are minimal. There is no documented risk of seizure associated with tDCS, but participants with a history of seizure disorder will be excluded to ensure optimum safety. Side effects associated with tDCS include mild headache, tingling, itching, or stinging under the electrodes, and skin irritation. After each therapy session, an aloe cream will be applied to the skin under the electrodes to reduce risks associated with skin drying.

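### The exclusion criteria cover earlier TMS treatment and deep brain stimulation but not earlier tDCS, leaving a small, avoidable threat to the sham blinding

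*Combined protocol and SAP*

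**What the plan says.** The first exclusion bullet in section 4 (Inclusion and Exclusion Criteria) begins with "Individuals with a clinically defined neurological disorder, with an increased risk of seizure for any reason" and goes on to say that those "with a history of treatment with TMS, deep brain stimulation for any disorder will be excluded". Earlier tDCS is not named there or in any other inclusion or exclusion criterion. The nearest other entry is "Hypersensitivity to electrical or magnetic stimulation". That removes people who react badly to stimulation, but not people who have had tDCS and tolerated it.

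On blinding, the Study Overview in section 5 says: "The proposed study is a double-blinded, randomized-control design". Under Study Interventions, "Participants will undergo 12 sessions (20-min each) of active or sham tDCS using 2mA current", and "for sham tDCS, the stimulator will be turned off automatically 30 s following the application". The stated basis for the credibility of the sham is this: "The sham stimulation mimics the transient scalp sensation perceived when the stimulator is initially switched on". The same paragraph describes the technique as current best practice for a convincing sham.

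The tDCS risk paragraph in section 8 adds: "Side effects associated with tDCS include mild headache, tingling, itching, or stinging under the electrodes, and skin irritation". It does not say how long these sensations last.

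The plan does not provide for recording earlier tDCS exposure or for asking participants to guess their allocation. The analysis in section 7 (Data Management) has group and time as its only factors.

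**The concern.** The list bars two kinds of earlier brain stimulation and leaves out the kind that the trial tests. Someone who has had a full active session may have a reference for how it feels beyond the first half minute. If so, that person might recognise the allocation more readily than a naive participant would.

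Recognition would matter most where the participant can influence the result. The FAAM is self-reported, and SEBT reach and side-hop time depend on effort. The stated hypothesis (section 3, Background) is that tDCS adds to balance training. A participant who recognises active stimulation might report or try more, and one who recognises sham might report or try less. Randomisation does not protect against this, because it arises after allocation. The pre-intervention measurement comes before any stimulation, so a shift would appear only at the 2-week and 4-week measurements. It would therefore enter the group-by-time interaction on which the analysis relies.

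**Working it through.** The plan states no figure on this point, so there is none to reproduce. The check has two parts.

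**1. Is a tDCS-experienced person eligible as written?**

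- *Criterion on earlier brain stimulation:* it names TMS treatment and deep brain stimulation only.
- *Hypersensitivity criterion:* it does not apply to someone who tolerated tDCS.
- *Neurological criteria:* these remove people with stroke, Parkinson's disease or another defined neurological disorder. They do not remove a healthy research volunteer or a patient with a musculoskeletal complaint.
- *Plausibility of such people presenting:* section 3 cites tDCS studies in chronic low back pain and in chronic ankle instability itself. Section 14 recruits from university campuses, community centers, and sports medicine and orthopedic clinics.

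Such a person is therefore eligible.

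**2. How large could the effect be?**

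Inputs:

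- N = 60 (section 15, Local Number of Subjects).
- p, the share of entrants with earlier tDCS. The documents do not give it; assumed range 0.5% to 10%.
- δ, the shift in an outcome when a participant recognises the allocation. Not given; assumed 0.5 SD, upward in the active arm and downward in the sham arm.
- Share of prior users who recognise their allocation. Not given; set to 100%, the extreme case.

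Formulas:

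- Expected prior users across both arms = N × p.
- The active-arm mean moves by +p × δ and the sham-arm mean by −p × δ, so the group difference moves by 2 × δ × p. With δ = 0.5 SD this is 2 × 0.5 × p = p, in SD units.

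| Assumed p | Expected prior users of 60 | Shift in group difference |
|---|---|---|
| 0.5% | 60 × 0.005 = 0.3 | 0.005 SD |
| 2% | 60 × 0.02 = 1.2 | 0.02 SD |
| 5% | 60 × 0.05 = 3 | 0.05 SD |
| 10% | 60 × 0.10 = 6 | 0.10 SD |

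The counts cover both arms. If the arms are equal, the expected number in the sham arm is half: 0.15 at the low end and 3 at the high end. If only a fraction of prior users recognise their allocation, the shift falls in proportion.

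For scale, section 15 plans on f = 0.55. If that is read as a two-group f with equal arms, d = 2 × 0.55 = 1.10. The largest shift in the table is then 0.10 / 1.10, about 9% of the planning effect, and the smallest is 0.005 / 1.10, about 0.5%. The documents do not say which effect f refers to, so this comparison is only a guide.

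**The case against.** The case on the other side is substantial.

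- **The criterion may be about safety.** Earlier TMS treatment and deep brain stimulation share a sentence with neurological disorder and seizure risk, and nothing in the protocol requires participants to be naive to tDCS. This stands: no two passages contradict each other, and the omission is not an error. It is still a gap that affects blinding.
- **Most tDCS-treated groups are already excluded.** Section 3 places the extensive use of tDCS in neurological patients. For musculoskeletal conditions it speaks only of growing interest and describes one back-pain study and one ankle-instability study. This also stands, and it is why the assumed prevalence range reaches well below 1%.
- **The sham may work for experienced people too.** If active stimulation is felt mainly at onset, memory of a full session offers little to compare. The protocol says that its sham is convincing, but gives no evidence for people with tDCS experience. The question stays open.
- **The neural outcomes are less exposed.** Hmax/Mmax and the motor-evoked potentials are evoked responses. This stands.
- **The screening questionnaires may ask.** Appendices A-C are not in the supplied text. Even if they ask, no listed criterion acts on the answer.
- **An allocation-guess question would do more.** It would test blinding in all participants, whereas the exclusion concerns only a few. That is a fair, complementary suggestion and does not remove the case for the exclusion.

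A reader might infer that the trial is almost bound to enrol a prior user and that its blinding is therefore compromised. The documents do not support that. They give no prevalence, and the chance of enrolling at least one such person does not measure bias.

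**Conclusion.** The gap is real and small. People with tDCS experience are eligible, and they might distinguish the 30 s sham from active stimulation better than naive participants. The FAAM, SEBT and side hop are the outcomes mainly at risk.

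Under the deliberately extreme assumption that every prior user recognises the allocation, the group difference moves by about 0.005 to 0.10 SD. That range rests on the assumed prevalence and the assumed shift per person, neither of which comes from the documents.

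Two stronger readings should be resisted. One is that experienced participants will identify the sham; nothing in the documents shows this. The other is that any bias must favour tDCS. That direction is plausible given the hypothesis, but a prior user may have received sham before or felt no benefit, and so may not expect active stimulation to be better. The point is a cheap improvement and does not call the design into question.

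**What to change.** In the first exclusion bullet of section 4, add *any previous tDCS, for treatment or in research* beside TMS treatment and deep brain stimulation. Add a matching question to the phone or email screen described under General Procedures in section 5, so that the criterion is applied before the baseline visit is booked.

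The cost is a few words, one screening question and a few volunteers lost. The interventions, measurements and analysis stay as they are.

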# 5) **Procedures Involved\***

## **Study Overview**

The proposed study is a double-blinded, randomized-control design which examines the efficacy of tDCS with balance training (BT) for patients with chronic ankle instability (CAI). Participants will be randomly allocated to one of two groups including (1) anodal tDCS + BT and (2) sham tDCS + BT. Outcome measures allow us to measure effects on postural balance, neural functions, and self-reported physical function.

#### **General Procedures**

Figure 1 illustrates the study flow, procedures and design. Participants will undergo brief screening over the phone or email to ensure they meet inclusion criteria. A faceto-face baseline assessment will be scheduled for eligible individuals at the Sports Medicine Laboratory in the Max Orovitz Building. Potential participants will be given a full description of the study procedures and asked to read and sign an IRBapproved informed consent form before any study procedures or assessments are conducted. Consent will take place in a private office and will be conducted by trained staff, including the principal investigator, co-investigator, research assistant. All participants who provide written consents will be screened for their current health status to determine whether they qualify for participating in the study. The screening involves several questionnaires to be administered by a certified athletic trainer to ensure eligibilities and safety of participants (Appendices A-C). For qualified participants, the certified clinician will perform a standard physical exam of the ankle joint and quantify a current level of physical activity using physical activity questionnaire (Appendix D-E). During the preintervention measurement, eligible participants will complete a battery of assessments including postural control, selfreported functions, and neural functions.

#### Figure 1. Flowchart of Overall Study Design and Procedure

There will be one screening day and 2 separate testing days (Figure 2). On the screening day, participants will fill out the CAIT and health questionnaire to determine the presence of CAI. On the first testing day, self-reported function (FAAM), static postural control, and neural excitability (H-reflex, TMS) will be measured. On the second testing day, dynamic postural control (SEBT and side hop) will be measured. The testing days will be separated by at least 24 hours (Figure 2). The testing will repeat at post-2-weeks and post 4-weeks of intervention measurement.

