# 7) Data Management\*

Data will be stored in a personal computer which is in locked research offices and is encrypted and password protected. The means and standard deviations will be calculated for one pre and two post outcome measures and will be used for statistical analysis. The normal distribution of data will be assessed by using the Shapiro-Wilk tests. For each outcome measures (postural control, neural measures, and self-

> reported function), 2 (group: anodal tDCS+BT and sham tDCS+BT) by 3 (time: preintervention, 2 weeks post-, 4 weeks post-intervention) ANOVA with repeated measures will be performed to determine effects of tDCS for each outcome measure. In the presence of a significant group-by-time interaction, a post-hoc analysis using Sidak adjustment will be conducted. The level of significance will be set a priori at 0.05. All statistical analyses will be performed using SPSS 26.0 statistical software (SPSS Incorporated, Chicago, IL, USA).

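### Do the procedures text and the ANOVA description place the two post-tests at different times?

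*Combined protocol and SAP*

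**What the plan says.** Three places in the combined protocol and SAP bear on the timing.

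- **Section 5 (Procedures Involved), under the Figure 1 caption:** "The testing will repeat at post-2-weeks and post 4-weeks of intervention measurement". This is the only sentence in the procedures that dates the repeat tests.
- **Section 7 (Data Management):** "The means and standard deviations will be calculated for one pre and two post outcome measures", and the time factor of the repeated-measures ANOVA is given as "time: preintervention, 2 weeks post-, 4 weeks post-intervention".
- **Section 5, Study Interventions:** "BT will be implemented 3 times a week over 4 weeks, each training session lasting about 20 minutes", and "Participants will undergo 12 sessions (20-min each) of active or sham tDCS using 2mA current". The course is therefore 4 weeks long.

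Section 5, General Procedures, also points the reader to a flowchart: "Figure 1 illustrates the study flow, procedures and design". That figure is not reproduced in the text available for this review.

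**The concern.** Two weeks of an intervention are counted from its first session. Two weeks after an intervention are counted from its last. With a 4-week course these are different visits, and no visible sentence says which clock is meant.

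The time factor is part of the only planned analysis, and pairwise comparisons follow only if the group-by-time interaction is significant. If the tests fall during and at the end of training, the interaction concerns the response to stimulation while it is being given and on completion. If they fall after training, it concerns how well any benefit is kept. A report that tested on the first schedule but used the section 7 labels would present a half-course test as a post-intervention result. If the section 7 labels are literal, neither test measures the effect at the end of training.

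**Working it through.** **Inputs.** Course length 4 weeks and 3 sessions per week (section 5, Study Interventions); tests at 2 and 4 weeks (section 5 under Figure 1, and section 7); 2 groups and 3 time levels (section 7).

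**Check on the course.** 3 sessions per week × 4 weeks = 12 sessions, which agrees with the stated number of tDCS sessions.

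**Clock from the first session** (natural reading of the procedures sentence):

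- First repeat test: week 2, after 3 × 2 = 6 sessions, 6/12 = 50% of the course.
- Second repeat test: week 4, after 3 × 4 = 12 sessions, 12/12 = 100%, 0 weeks after training.

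**Clock from the last session** (literal reading of section 7):

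- First repeat test: 4 + 2 = week 6, after 12 sessions, 2 weeks after training.
- Second repeat test: 4 + 4 = week 8, after 12 sessions, 4 weeks after training.

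**Difference.** 6 − 2 = 4 weeks for the first test and 8 − 4 = 4 weeks for the second. One of the two tests is at the end of training under the first clock, and none under the second.

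**Can the phrases agree?** Each has two possible readings:

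| Procedures sentence | Section 7 labels | Result |
|---|---|---|
| After 2 and 4 weeks of training | Shorthand for the same | Agree: weeks 2 and 4 |
| Garbled form of a post-intervention measurement | Literal | Agree: weeks 6 and 8 |
| After 2 and 4 weeks of training | Literal | Conflict |
| Garbled form of a post-intervention measurement | Shorthand | Conflict |

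The texts share the same two numbers, the same count of repeat tests and the same prefix (post) on both. Weeks 6 and 8 are stated nowhere in the documents; they appear only when 4 weeks are added to the section 7 labels. The conflict that prompts the concern, in the third row, arises when an ungrammatical sentence is tidied in one direction and a compressed label is taken to the letter.

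**What changes in the analysis.** The group-by-time interaction has (2 − 1) × (3 − 1) = 2 degrees of freedom under either clock. For any test time t, the arm contrast is the change from baseline to t on active stimulation minus the change from baseline to t on sham. Since t is common to both arms, the choice of clock does not bias the contrast. The alpha of 0.05 and the sample-size calculation in section 15 do not refer to a particular visit, so the wording leaves them alone.

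**The case for a change.** The strongest case for acting is that the time levels help define what the trial estimates. If a sentence can be read two ways, the visible text has not fixed the schedule. Staff booking TMS, H-reflex and balance visits need one reference point. Even a clear flowchart would leave at least one of the two sentences open to misreading, and the cure would cost only a few words.

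Part of this stands. The two phrases do differ, the session arithmetic is right, and the visible text does not name the starting point. The interpretation of a positive interaction does depend on the answer.

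The step from there to a defect in the plan does not stand. The flowchart is where a visit schedule would normally be drawn, and its absence from this copy cannot be counted as an omission. The harm needs a further event that the plan does not call for: testing on one schedule and then reporting with the other schedule's label. The documents contain no wording for the trial's conclusions, and the objective in section 2 speaks only of an effect of training with stimulation. It commits the investigators to neither an end-of-training claim nor a retention claim.

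**Conclusion.** This is an ambiguity of wording that the investigators will resolve in practice, and it calls for no change to the plan. At most it moves each repeat test by 4 weeks between readings. It leaves unchanged the number of tests (two), the 2 by 3 model, the interaction degrees of freedom (2), alpha and the planned sample size, and it introduces no bias between arms. Harmonising the words would restate the intended schedule without altering any visit, test or result.

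The conclusion rests on three assumptions. All participants in both arms are tested on one common schedule, which is plausible for a study run in a single laboratory. The investigators, who know when testing took place, describe the time points accordingly when they report. And the unseen flowchart does not itself contradict both texts. Which schedule was intended cannot be decided from the visible text, and the validity of the arm comparison does not depend on it.
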